2.4.1 Administration of Investigational Product

Subjects randomized to the combination arm of IVIG plus standard medical treatment, will receive IV Gamunex-C. Gamunex-C will be administered intravenously (peripheral or central vein) through a separate infusion line. It is recommended that Gamunex-C infusion should commence at an infusion rate of 0.5 mg/kg/minute (0.005 mL/kg/min) for approximately 30 minutes. If the infusion is well tolerated, the rate of administration may be increased to a maximum of 4 mg/kg/minute (0.04 mL/kg/minute) as follows: the rate may be increased by doubling the infusion rate after intervals of not less than 15-30 minutes, so long as the infusion remains well tolerated. For subjects judged to be at risk for renal dysfunction

GRIFOLS Bioscience Industrial Group	Number	BLG-CL-PRT-000020	Version	4.0	Status	Effective	Effective Date	19-Jul-2021
	GC2007 - A Multicenter, Randomized, Open-label Parallel Group Pilot Study to Evaluate Safety and Efficacy of High Dose Intravenous Immune Globulin (IVIG) plus Standard Medical Treatment (SMT) versus SMT alone in					Page		27 of 91

or thrombosis, Gamunex-C infusion should be at the minimum infusion rate practicable. If adverse events (AEs) occur, the rate may be reduced or the infusion interrupted until symptoms subside. Lack of tolerance at any given rate must be recorded as an AE at that rate. The infusion may then be resumed at the rate that is tolerable for the subject.

The total net dose of 2 g/kg body is capped to a maximum of 160 g for subjects weighing more than 80 kg. The dose of 2g/kg will be administered in divided doses over consecutive days. At the discretion of the Principal Investigator, the 2 g/kg net total dose may be divided either into (a) infusions of 500 mg/kg body weight over 4 days OR (b) 400 mg/kg body weight over 5 days.

To calculate the dose for each infusion, multiply the weight of the subject (kg) by the dose in mg/kg. For example, a 70 kg individual dosed for 5 days at 400 mg/kg per infusion will receive 28 g per day. For Gamunex-C 10%, multiply the number of grams for the subject's infusion by 10 mL/gram to obtain the number of milliliters (mL) of Gamunex-C to be infused IV each day (in this example the amount is 280 mL daily for 5 days).

Gamunex-C should be infused using a separate line by itself, without mixing with other intravenous fluids or medications the subject might be receiving. The Gamunex-C infusion line can be flushed with 5% dextrose in water or 0.9% sodium chloride for injection. Do Not flush with heparin.

Subjects in the SMT alone arm will receive all standard of care interventions required.

2.4.2 Justification for Selection of Doses/Timing of Investigational Product

The dose of Gamunex-C selected for this study is commensurate with that employed to abrogate autoimmune phenomena and attenuate symptoms of neurological disorders. Gamunex-C dosages for various medical conditions for which high doses are prescribed are summarized in [Table 2-2](#) across the 57 countries wherein IGIV-C is approved.

Table 2-2 Immunomodulatory Doses of IGIV-C Worldwide (Development Safety Update Report 2019)

Indication	Administration
*Primary immune thrombocytopenia (ITP)	Total dose of 2 g/kg divided in 2 doses of 1 g/kg for 2 consecutive days or into 5 doses (400 mg/kg) for 5 consecutive days
Guillain Barré syndrome	400 mg/kg on 3 to 7 consecutive days
Kawasaki disease	1.6- 2 g/kg as a single infusion or divided doses over 2 to 5 days
*Chronic inflammatory demyelinating polyneuropathy (CIDP)	Loading dose: 2 g/kg in divided doses over 2 to 4 days Maintenance dose: 1 g/kg over 1 day or in 2 divided doses over 2 consecutive days, every 3 weeks

GRIFOLS Bioscience Industrial Group	Number	BLG-CL-PR7-000020	Version	4.0	Status	Effective	Effective Date	19-Jul-2021	Page	28 of 91										
	GC2007 - A Multicenter, Randomized, Open-label Parallel Group Pilot Study to Evaluate Safety and Efficacy of High Dose Intravenous Immune Globulin (IVIG) plus Standard Medical Treatment (SMT) versus SMT alone in Multifocal motor neuropathy (MMN)																			
*Indicates FDA approved indications.																				
Reference: Development Safety Update Report IGIV-C (version 8; July 2019).																				
Subjects randomized to the combination arm of IVIG plus SMT will receive a total dose of 2 g/kg of Gamunex-C administered in divided doses over 4 or 5 days.																				
<h2>2.5 Compliance Statement</h2> 
This study will be conducted under the conditions described in this protocol and in compliance with the International Council for Harmonisation of Technical Requirements for Pharmaceuticals for Human Use (ICH) Good Clinical Practice (GCP) and all applicable regulatory requirements.
																				
<h2>2.6 Study Population</h2> 
The purpose of this study is to determine if high dose IVIG plus SMT can reduce the proportion of subjects dying through Day 29 versus SMT alone in hospitalized subjects with COVID-19 requiring ICU admission.
																				

Approximately 100 subjects will be randomized (1:1) with an interim analysis after 50 subjects (approximately 25 per group). There will be no interruption in study conduct during the interim analysis as this simply represents sponsor safety due diligence.
																				
<h2>2.7 Relevant Data and Literature Review</h2> <h3>2.7.1 COVID-19 Therapeutic Approaches</h3> 
Coronaviruses (CoVs) typically affect the respiratory tract of mammals, including humans, and lead to mild to severe respiratory tract infections. In the past two decades, two highly pathogenic human CoVs (HCoVs), including severe acute respiratory syndrome coronavirus (SARS-CoV) and Middle East respiratory syndrome coronavirus (MERS-CoV), emerging from animal reservoirs, have led to global epidemics with high morbidity and mortality.
																				

Several studies demonstrate that cells infected by SARS-CoV produce elevated levels of pro-inflammatory cytokines (PICs) in order to combat the invading viruses. However, the overproduced PICs (including monocyte chemoattractant protein-1 [MCP-1], transforming growth factor β 1 [TGF-β1], tumor necrosis factor-α [TNF-α], interleukins- 1β and -6 [IL-1β, and IL-6]), may cause immuno-mediated damage to the lungs and other organs, resulting in acute lung injury (ALI) and ARDS (He et al., 2006; DeDiego et al., 2014).
																				

The elevated levels of PICs in blood released from the SARS-CoV-infected cells and the uninfected cells stimulated by viral antigens or some PIC-regulatory factors, eg Nuclear Factor-kappaB (NF-κB) and p38 (a mitogen-activated protein kinase) (He et al., 2006; DeDiego et al., 2014), may damage the cells in the lungs and other organs. In addition, blood hypo-oxygenation due to ARDS and disseminated intravascular coagulation resulting from
																				

GRIFOLS	Number	Big-CL-PRT-000020	Version	4.0	Status	Effective	Effective Date	19-Jul-2021
	GC2007 - A Multicenter, Randomized, Open-label Parallel Group Pilot Study to Evaluate Safety and Efficacy of High Dose Intravenous Immune Globulin (IVIG) plus Standard Medical Treatment (SMT) versus SMT alone in Bioscience Industrial Group					Page		29 of 91

impairment of microvessel endothelial cells may further damage the structure and function of different organs in SARS patients, resulting in multi-organ dysfunction.

The ACE2 expressing cells are the primary targets for SARS-CoV infection in humans initiating a massive cascade of pro-inflammatory cytokines via macrophages over-activation causing ARDS. High levels of PICs are expressed in the SARS-CoV-infected ACE2+ cells, but not in the uninfected cells (He et al., 2006).

Therefore, application of PIC antagonists may reduce the severity and mortality of SARS and may potentially reduce other pathogenic human coronaviruses (He et al., 2006; DeDiego et al., 2014; Tse et al., 2004). In the current study, it is considered that the immunomodulatory properties of high dose IVIG (Gamunex-C) may attenuate the deleterious effects of cytokine release syndrome engendered in COVID-19.

Currently, there are no approved treatments for COVID-19 in Europe or the United States. The lack of disease-directed therapeutic options has led to urgent interventions in anticipation of some potentially promising effects. Some antivirals are currently under evaluation. These include favipirivir (AVIGAN) manufactured by Fujifilm in Japan, Gilead's remdesivir, and Kaletra® (lopinavir/ritonavir) commercially available for human immunodeficiency virus (HIV). Although Kaletra did not show demonstrable efficacy in a recently reported study in China (Cao et al., 2020), additional trials are underway. There are also investigations of chloroquine and hydroxychloroquine as treatment modalities and potential applications for post-exposure prophylaxis according to Clinicaltrials.gov and other clinical trial registries. While both remdesivir and chloroquine phosphate/hydroxychloroquine sulfate have EUAs before licensure in the United States, efficacy remains to be further defined. Initial results for remdesivir are most encouraging. The NIAID Adaptive COVID-19 Treatment Trial, showed that subjects receiving remdesivir had a shorter median time to recovery compared with those receiving placebo (11 vs 15 days; $p<0.001$) with a trend toward a survival benefit, and mortality rate of 8.0% vs 11.6% by day 29 ($p=0.06$) (Fact Sheet Remdesivir EUA 1 May 2020). A smaller randomized study from China did not show a significant benefit for remdesivir in a similar hospitalized population (hazard ratio for time to clinical improvement 1.23 [95% CI 0.87–1.75]); however, that trial was stopped early due to slow enrolment and power was substantially less than planned (58% instead of 80%) (Wang, Zhang et al., 2020).

To date there are still no confirmed specific disease modifying agents. Therefore, the potential therapeutic benefit conveyed by the immunomodulatory effects of high dose IVIG warrants clinical investigation. This is particularly true given the urgency and extent of the COVID-19 pandemic.

GRIFOLS	Number	BLG-CL-PRT-000020	Version	4.0	Status	Effective	19-Jul-2021	Effective Date	19-Jul-2021
	GC2007 - A Multicenter, Randomized, Open-label Parallel Group Pilot Study to Evaluate Safety and Efficacy of High Dose Intravenous Immune Globulin (IVIG) plus Standard Medical Treatment (SMT) versus SMT alone in Bioscience Industrial Group							Page	30 of 91

3 STUDY OBJECTIVES AND PURPOSE

3.1 Efficacy Objectives

3.1.1 Primary Efficacy Objective

To determine if high dose IVIG plus SMT can reduce all-cause mortality versus SMT alone in hospitalized subjects with COVID-19 requiring admission to the ICU through Day 29.

3.1.2 Secondary Efficacy Objectives

The secondary efficacy objective includes:

- To compare high dose IVIG plus SMT versus SMT alone with regard to clinical efficacy as assessed by clinical severity, duration of hospital and ICU stay, dependency on oxygen and ventilatory support, and clinical response criteria including National Early Warning Score (NEWS), clinical status scale, and Sequential Organ Failure Assessment Score (SOFA) through Day 29 in hospitalized subjects ill with COVID-19 requiring admission to the ICU.

3.1.3 Exploratory Efficacy Objectives

The exploratory objectives of this study are:

- To evaluate the effect of high dose IVIG plus SMT versus SMT alone with regard to quantitative severe acute respiratory syndrome coronavirus 2 (SARS-CoV-2) viral load and anti-SARS-CoV-2 antibodies in hospitalized subjects with COVID-19.
- To evaluate whether high dose IVIG plus SMT versus SMT alone reduces the frequency of hyperinflammation based on a pre-specified biochemical definition through Day 29.
- To evaluate cytokine profile changes from baseline for high dose IVIG plus SMT versus SMT alone through Day 29.

3.2 Safety Objective

To determine the safety and tolerability profile through Day 29 of high dose IVIG plus SMT versus SMT alone in hospitalized subjects with COVID-19.

4 STUDY DESIGN

4.1 Primary Endpoint and Secondary Endpoints

4.1.1 Primary Efficacy Endpoint

The primary efficacy endpoint is all cause mortality rate through Day 29.

GRIFOLS Bioscience Industrial Group	Number	BLG-CL-PRT-000020	Version	4.0	Status	Effective	Effective Date	19-Jul-2021
	GC2007 - A Multicenter, Randomized, Open-label Parallel Group Pilot Study to Evaluate Safety and Efficacy of High Dose Intravenous Immune Globulin (IVIG) plus Standard Medical Treatment (SMT) versus SMT alone in					Page		31 of 91

4.1.2 Secondary Efficacy Endpoints

Secondary efficacy endpoints include the following:

- Time to actual ICU discharge: defined as duration of ICU stay from Day 1 through Day 29
 - Additionally, time to a medical equivalence of ICU discharge will be recorded and analyzed (defined as the time point when the patient no longer requires ICU level care, i.e., not requiring invasive mechanical ventilation, or intensive monitoring such as arterial line or central line placement, administration of IV vasopressors to support blood pressure, or O₂ supplementation greater than that delivered by nasal cannula)
- Duration of mechanical ventilation from Day 1 through Day 29
- Time to actual hospital discharge: defined as duration of hospitalization from Day 1 through Day 29
 - Additionally, time to a medical equivalence of hospital discharge will be recorded and analyzed (defined as the time point when the patient no longer requires supplemental oxygen and no longer requires ongoing medical care [yet may not be discharged from hospital for social or quarantine reasons])
- Duration of any oxygen use from Day 1 through Day 29
- Absolute value and mean change from baseline in the Ordinal scale Day 1 through Day 29

The Ordinal scale is as follows:

- 1) Death;
- 2) Hospitalized, on invasive mechanical ventilation or extracorporeal membrane oxygenation (ECMO);
- 3) Hospitalized, on non-invasive ventilation or high flow oxygen devices;
- 4) Hospitalized, requiring supplemental oxygen;
- 5) Hospitalized, not requiring supplemental oxygen;
- 6) Not hospitalized, limitation on activities;
- 7) Not hospitalized, no limitations on activities.

- Proportion (percentage) of subjects in each severity category of the 7-point Ordinal scale at Day 15 and Day 29
- Number of subjects who develop Acute Respiratory Distress Syndrome (ARDS) overall and distribution by severity through Day 29 ([Appendix 3](#))
- Change from baseline in Sequential Organ Failure Assessment (SOFA) score at Day 5, Day 15, and Day 29 ([Appendix 4](#))

GRIFOLS Bioscience Industrial Group	Number	BLG-CL-PRT-000020	Version	4.0	Status	Effective	Effective Date	19-Jul-2021
	GC2007 - A Multicenter, Randomized, Open-label Parallel Group Pilot Study to Evaluate Safety and Efficacy of High Dose Intravenous Immune Globulin (IVIG) plus Standard Medical Treatment (SMT) alone in						Page	32 of 91

- Assessment of Clinical Severity: Change in NEWS from baseline (Day 1 through Day 29)

The NEWS has demonstrated an ability to discriminate patients at risk of poor outcomes. This score is based on 7 clinical parameters (respiration rate, oxygen saturation, any supplemental oxygen, temperature, systolic blood pressure, heart rate, level of consciousness [Alert, Voice, Pain, Unresponsive]).

<https://www.mdcalc.com/national-early-warning-score-news> (Appendix 2)

- Time to clinical response: NEWS ≤ 2 maintained for 24 hours, Day 1 through Day 29

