All subjects will be followed daily through Day 10. After Day 10, if subjects are discharged from the hospital, evaluations at Day 15 and 29 are required. Berlin criteria for ARDS ([Appendix 3](#)) and SOFA score ([Appendix 4](#)) will be assessed on Day 1, 5, 15, and 29. Subjects remaining hospitalized will be followed daily through Day 29. Days 15±1 and 29±1 may be performed at the study site or, if deemed appropriate, at an alternate site (e.g., subject's residence, local healthcare professional's site) under the care and supervision of trained healthcare personnel. If an in-person visit is unable to be conducted for Day 15 or

GRIFOLS Bioscience Industrial Group	Number	BLG-CL-PR7-000020	Version	4.0	Status	Effective	Effective Date	19-Jul-2021
	GC2007 - A Multicenter, Randomized, Open-label Parallel Group Pilot Study to Evaluate Safety and Efficacy of High Dose Intravenous Immune Globulin (IVIG) plus Standard Medical Treatment (SMT) versus SMT alone in						Page	34 of 91

Day 29, the study site will make a phone call to the subject to obtain as much information as possible remotely (e.g., Ordinal Scale, clinical features key symptoms, supplementation oxygen use, SAEs and TEAEs, concomitant medications). Phone Checks will occur at Day 60 and Day 90 for vital status (living or deceased), any hospital re-admissions or serious/non-serious adverse events after the Day 29 Final Clinic Visit. Details are provided in [Appendix 1](#) (Schedule of Study Procedures). Clinical status will be evaluated for all hospitalized subjects daily with vital signs, Ordinal Scale (7 categories analogous to Cao et al. 2020), and NEWS at Screening/Baseline and during IVIG plus SMT or SMT alone treatment and during Follow-up. The NEWS calculation is delineated in [Appendix 2](#) and can be calculated using the on-line web tool at <https://www.mdcalc.com/national-early-warning-score-news> .

For subjects in the combination arm (IVIG plus SMT) all laboratory samples must be drawn prior to infusion of IVIG, if laboratory assessments are required for a day in which IVIG is being infused.

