5.3.4 Follow-up of Subjects Withdrawn from Study

For subjects administered any amount of IP (infusion) who discontinue the clinical trial, and for subjects randomized to SMT alone, details for follow-up are delineated below.

For subjects who withdraw from the clinical trial (excluding screen failures), study procedures and assessments scheduled for the Day 15 Visit will be performed at the time of withdrawal, during an unscheduled visit at the time of withdrawal. In addition, to assure major clinical outcomes are adequately captured as a measure of overall safety, these subjects will be asked to return for their chronological Day 29 Clinic Visit (ie, 28 days after Day 1 baseline), unless the unscheduled visit is within 4 days of their chronological Day 29 visit, and provided that they or their legally acceptable representative have not withdrawn consent. At the chronological Day 29 Clinic Visit, all assessments will be performed *except for* central laboratory testing: cytokine panel, respiratory sample for quantitative measurement of SARS-

GRIFOLS Bioscience Industrial Group	Number	BLG-CL-PRT-000020	Version	4.0	Status	Effective	Effective Date	19-Jul-2021	44 of 91
	GC2007 - A Multicenter, Randomized, Open-label Parallel Group Pilot Study to Evaluate Safety and Efficacy of High Dose Intravenous Immune Globulin (IVIG) plus Standard Medical Treatment (SMT) versus SMT alone in								

CoV-2 viral load (obtained via nasopharyngeal swab), and quantitative measurement of IgM and IgG antibodies, which are not required for these subjects at chronological Day 29 for premature withdrawals. These subjects will also have Phone Checks at Day 60 and Day 90 for vital status (living or deceased), and any hospital re-admissions or serious/non-serious adverse events after the Day 29 Final Clinic Visit.

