- Record details of mechanical ventilation parameters (start/end date/time)
- Record oxygen saturation (specify on or off oxygen supplementation)
- Record daily 24-hour fluid balance (intake and output) while in hospital
- Record body weight for assessing fluid balance twice daily on Days 1 through 5 inclusive (at least 8 hours should separate the time from the first recorded weight)

GRIFOLS Bioscience Industrial Group	Number	BLG-CL-PRT-000020	Version	4.0	Status	Effective	Effective Date	19-Jul-2021	Page	51 of 91
	GC2007 - A Multicenter, Randomized, Open-label Parallel Group Pilot Study to Evaluate Safety and Efficacy of High Dose Intravenous Immune Globulin (IVIG) plus Standard Medical Treatment (SMT) versus SMT alone in									

- Record SAEs and TEAEs
- Record standard care concomitant medications

All laboratory tests and serum and plasma samples are required for all study subjects, regardless of treatment assignment. For subjects randomized to IVIG plus SMT all laboratory samples must be obtained prior to the Gamunex-C infusion on the designated day.

On Day 5 ± 1 day the following *additional* assessments will be performed:

- Assessment of ARDS (Berlin Criteria) ([Appendix 3](#))
- SOFA score ([Appendix 4](#))
- Respiratory sample for quantitative measurement of SARS-CoV-2 viral load by NAT or PCR (real-time RT-PCR) (obtained via nasopharyngeal swab)
- Sample for quantitative measurement of IgM and IgG antibodies to SARS-CoV-2 (store serum samples frozen at -70°C for later analysis at an external lab)
- Serum Chemistry (creatinine, albumin, ALT, total bilirubin, LDH)
- Ferritin (serum), D-dimer (plasma, sodium citrate tube), CRP (serum)
- Hematology: absolute lymphocyte count and standard hematology (hemoglobin, hematocrit, platelet count, leukocyte count with differential)
- DAT
- Cytokine panel (IL-1 β , IL-10, IL-6, IL-8, IL-2, interferon γ , and TNF- α). Note: serum samples must be stored at -70°C for later analysis at a reference laboratory.

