7.2.4 Day 11-14 for Subjects Still Hospitalized: SMT and Daily Evaluations

All subjects receive continued SMT.

Daily assessments include the following:

- Ordinal Scale assessment
- NEWS ([Appendix 2](#))
- Clinical features key symptoms: fever, cough, shortness of breath, fatigue, myalgia etc.
- Vital signs (temperature, systolic and diastolic blood pressure, pulse, respiratory rate)
- Record any supplemental oxygen administration (type, %, flow start/end date/time)
- Record details of mechanical ventilation parameters (start/end date/time)
- Record oxygen saturation (specify on or off oxygen supplementation)
- Record SAEs and TEAEs
- Record standard care concomitant medications

GRIFOLS Bioscience Industrial Group	Number	BIG-CL-PRT-000020	Version	4.0	Status	Effective	Effective Date	19-Jul-2021	Page	52 of 91
	GC2007 - A Multicenter, Randomized, Open-label Parallel Group Pilot Study to Evaluate Safety and Efficacy of High Dose Intravenous Immune Globulin (IVIG) plus Standard Medical Treatment (SMT) versus SMT alone in									

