### **Number of subjects developed ARDS**

Berlin criteria for ARDS will be assessed on Days 1, 5, 15, and 29. The presence of ARDS and the degree of ARDS by Berlin criteria (Mild, Moderate, Severe) will be tabulated by treatment group at each visit.

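### The ARDS endpoint is worded as a cumulative count through Day 29, but Berlin criteria are scheduled on only three post-baseline days and the SAP tabulates them visit by visit, so the plan delivers point prevalence.

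*Protocol*

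**What the plan says.** The endpoint in Protocol 4.1.2, repeated in Protocol 7.1.2 and SAP 2.2.2, is "Number of subjects who develop Acute Respiratory Distress Syndrome (ARDS) overall and distribution by severity through Day 29".

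On timing, Protocol 4.2 says that the Berlin criteria and the SOFA score "will be assessed on Day 1, 5, 15, and 29", and SAP 6.2 agrees: "Berlin criteria for ARDS will be assessed on Days 1, 5, 15, and 29". The item "Assessment of ARDS (Berlin Criteria") is in the Day 1 list (Protocol 7.2.2). It returns as an additional Day 5 item (7.2.3) and in the Day 15 and Day 29 lists (7.2.5, 7.2.7). It is absent from the daily lists for Days 2-10, 11-14 and 16-28. Those lists do include oxygen use, saturation, NEWS, the ordinal scale and ventilation, for example "Record details of mechanical ventilation parameters (start/end date/time").

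The whole planned analysis is one sentence in SAP 6.2: "The presence of ARDS and the degree of ARDS by Berlin criteria (Mild, Moderate, Severe) will be tabulated by treatment group at each visit".

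Two other provisions affect who is assessed:

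- Subjects who withdraw get an extra assessment, because "study procedures and assessments scheduled for the Day 15 Visit will be performed at the time of withdrawal" (Protocol 5.3.4).
- If a Day 15 or Day 29 visit cannot be held in person, "the study site will make a phone call to the subject to obtain as much information as possible remotely" (Protocol 4.2). Berlin status is not among the examples given of what to collect by phone.

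**The concern.** Counting subjects who develop a condition by Day 29 requires knowing, for each subject, whether it occurred on any day up to then. Three looks after baseline show only whether it was present on those days. The neighbouring SOFA endpoint is worded as change at Days 5, 15 and 29, which matches its schedule. The ARDS endpoint is not worded that way.

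Three things are at stake:

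- Subjects whose ARDS falls between looks are left out of the count, and the worst grade between looks is lost.
- ARDS already present on Day 1 is not separated from new ARDS.
- Death removes a subject from later looks. The ARDS comparison between arms therefore depends on mortality, which is the primary outcome, in a way the plan neither describes nor displays.

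**Working it through.** The documents give no ARDS rate, onset pattern, duration or power figure, so there is no planned number to reproduce. The check has four steps.

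**1. Coverage of the schedule (documents only).** Post-baseline days are Days 2-29, which is 28 days. Three carry a Berlin assessment: 3/28 = 10.7%. The 25 unassessed days form three gaps: Days 2-4 (3 days), 6-14 (9 days) and 16-28 (13 days).

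**2. Whether any other provision fills the gaps (documents only).**

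- SAP 6.2 has no look-back, cumulative count, worst-grade rule, exclusion of ARDS present on Day 1, or rule for death between visits.
- SAP 4.4 promises worst-case imputation for binary efficacy endpoints and refers to Section 6 for details. Section 6 gives none for ARDS.
- Daily oxygen, saturation and ventilation data are collected, but nothing derives ARDS from them. Under Protocol Appendix 3, Berlin grading needs imaging, PaO2/FiO2 and PEEP, and SpO2 may not be substituted in ventilated subjects.
- AEs and SAEs are collected (Protocol 8.3.8), but nothing feeds them into this endpoint.
- The assessment at withdrawal does not help a subject who dies between visits.

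**3. Share missed with fixed durations (assumed).** An episode with onset on day o and length D occupies days o to o + D − 1. It is missed if it contains none of Days 5, 15 and 29, that is, if it fits inside one gap. A gap of g days holds max(0, g − D + 1) such onsets. Onset is taken as equally likely on each day of the stated range.

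| D (days) | Onset Days 2-14: gaps of 3 and 9 | Onset Days 2-29: gaps of 3, 9 and 13 |
|---|---|---|
| 3 | (1 + 7)/13 = 62% | (1 + 7 + 11)/28 = 68% |
| 5 | (0 + 5)/13 = 38% | (0 + 5 + 9)/28 = 50% |
| 7 | (0 + 3)/13 = 23% | (0 + 3 + 7)/28 = 36% |
| 10 | 0/13 = 0% | (0 + 0 + 4)/28 = 14% |
| 14 | 0/13 = 0% | 0/28 = 0% |

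Moving each visit by up to one day changes the 7-day figures to 8-38% (onset Days 2-14) and 32-43% (onset Days 2-29).

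**4. Share captured with variable durations, and the part played by death (assumed).** This is a simulation with onset uniform over Days 2-14, mean duration 6-14 days in survivors, mean 4-10 days from onset to death, and 20-60% of cases fatal. An episode is captured if ARDS is present, with the subject alive, on Day 5, 15 or 29.

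- Exponential times: capture is 45-74% over the grid if a fatal case cannot be observed on the day of death, and 51-76% if it can. The overall range is about 45-76%.
- Less dispersed times (gamma, shape 4) with both means at 10 days: capture is about 85-87%.
- Death faster than recovery (exponential, means 4 and 10 days): capture falls from 63% to 56% to 50% as case fatality goes from 20% to 40% to 60%.
- Equal means (10 and 10 days), day of death observable: capture is flat at about 70%.
- Death slower than recovery (means 10 and 6 days), day of death observable: capture rises from about 60% to 65% as case fatality goes from 20% to 60%.

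To put the faster-death case in subjects, assume a true incidence of new ARDS of 40% in both arms, with case fatality of 20% in one and 40% in the other. Observed incidence is 0.40 × 0.63 = 25% against 0.40 × 0.56 = 22%. With about 50 subjects per arm, that is 12.6 against 11.2, a gap of between one and two subjects.

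**The case against.** The strongest reply is that the size of the loss is not established, and most of this reply stands. Fixed 10-day episodes with onset over Days 2-14 are never missed at nominal visit days. The exponential model produces many very short episodes, and nothing in the documents supports that shape. Subjects enter within 48 hours of starting ICU treatment, or once ICU admission has been decided, with infiltrates and a need for oxygen or ventilation. ARDS on Day 1 or soon after is therefore at least as plausible as onset spread evenly to Day 14. A reader might infer that a large share of new ARDS must be missed; the documents do not support that.

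A reader might also infer that the arm with more deaths will be credited with less ARDS. That holds only if death follows onset faster than recovery does. Other assumptions give no difference or the reverse.

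Nor is it right to infer that such episodes leave no record. Ventilation, oxygen and the ordinal scale are recorded daily in hospital, fatal and life-threatening AEs are SAEs, and ARDS is not among the listed COVID-19 symptoms kept out of TEAEs. A death is counted in the primary endpoint in any case.

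Finally, this is an untested secondary endpoint in an exploratory pilot, and retrospective look-back at unblinded sites has its own bias. Both points limit the weight of the matter and shape the fix. Neither removes the mismatch between a cumulative endpoint and visit-by-visit prevalence.

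**Conclusion.** The mismatch rests on the documents alone. The endpoint is a cumulative count of subjects who develop ARDS, with severity. The collection and the analysis give presence and degree on Days 1, 5, 15 and 29 among subjects alive and assessed. Episodes wholly inside a gap are not captured by the assessment that feeds the endpoint, and re-tabulating the four visits cannot recover them.

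The size is conditional on ARDS durations and onset times that the documents do not give. It runs from no loss, for fixed episodes of 10 days or more with onset by Day 14, to more than half, for 3-day episodes or the least favourable exponential settings. That missed ARDS can depend on mortality is established; the direction is not, and in the worked example the effect is one or two subjects. The plan should be corrected before analysis, but the primary endpoint is not affected.

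**What to change.** **In SAP 6.2:** define new ARDS as Berlin criteria met after Day 1 in subjects without ARDS on Day 1. Count it cumulatively through Day 29 with the worst grade reached, and show deaths without recorded ARDS as a separate category by arm.

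**In the eCRF:** add one look-back item at Days 5, 15 and 29 and at death or discharge, asking whether Berlin criteria were met since the last assessment, with first date and worst grade. It would be completed from blood gases, ventilator settings and imaging already in the chart. Withdrawal already triggers a Berlin assessment, which can carry the same item.

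**Keep the scheduled-visit table** as a sensitivity display. The look-back is retrospective, is made at unblinded sites, and depends on which tests clinicians ordered, so its completeness could differ between arms. The scheduled assessments fall on the same days in both arms.

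**If the look-back is not adopted:** restate the endpoint in the protocol and SAP as ARDS present at Days 5, 15 and 29 among subjects alive and assessed, with deaths shown separately.

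The cost is one eCRF item, a chart review at existing contacts and a paragraph in the SAP. No new test or visit is needed. The fallback costs only wording.
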